1.2 SCHEMA

2 INTRODUCTION

2.1 BACKGROUND & STUDY RATIONALE

Alzheimer's disease affects 6.2 million individuals in the United States and results in an annual cost of care of \$355 billion, including \$239 billion in Medicare and Medicaid payments combined ("2021 Alzheimer's disease facts and figures," 2021). People living with dementia (PLWD) often receive poorly coordinated and fragmented care that can lead to ineffective care and poor health outcomes, including trips to the emergency department and hospitalizations (Hirschman & Hodgson, 2018). Care for PLWD is demanding and stressful, as the needs of those with dementia are constantly evolving as their behavior and abilities change. Caregivers often experience mental health concerns such as anxiety and depression, poor physical health, compromised immune system, and emotional and social issues due to the demands and stress of caregiving (Elliott, Burgio, & DeCoster, 2010; Ferrara et al., 2008).

Multicomponent non-pharmacological psychosocial care interventions such as REACH (Resources for Enhancing Alzheimer's Caregiver Health), or NYUCI (NYU Caregiver Intervention) include more than one care technique or delivery method to foster support, expertise, information, or skills for caregivers to improve caregiver quality of life and health outcomes. These interventions usually include therapy and social support, education, supportive feedback, goal setting, and planning, as well as relaxation and physical exercises. These are offered as structured approaches to develop skills for problem solving, improving communication and improve relationships for caregivers and PLWD. These approaches have been recognized as high priority in the Alzheimer's research community to study the real-world effectiveness and implementation across different health care settings (Larson & Stroud, 2021). The multicomponent interventions such as REACH, NYUCI have been shown to reduce stress, improve depression, well-being of caregivers and delays nursing home placement of PLWD (OUT, 2018). Key challenges to these interventions include implementation, identifying & tailoring interventions to specific level of dementia and care partner support, and efficacy of caregiver-related interventions (Gaugler, Jutkowitz, & Gitlin, 2020; Hodgson & Gitlin, 2021). REACH-TX was effective in improving quality of life and decreasing caregiver burden when administered by a community agency, as there were

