4 STUDY DESIGN

4.1 OVERALL DESIGN

This is a feasibility/pilot, prospective cohort study to determine how to implement and refine Outreach-ER intervention for a larger clinical study.

Aim 1

To assess the feasibility and acceptability of Outreach-ER. This aim will be accomplished by collecting detailed process data which will allow the assessment of registration, enrollment, retention, and adherence/fidelity to the program. This is an important step prior to moving forward with a larger trial. We will also utilize mixed methods approach, including semi-structured interviews and surveys to assess the acceptability and experience of participants.

Aim 2

To assess feasibility of collecting outcomes and explore the effectiveness of Outreach-ER. In care partners, we will evaluate the pre-post benefits of Outreach-ER to improve mood (Center for Epidemiologic Studies Depression Scale-10), reduce burden (Zarit Burden Interview-12), reduce stress (Perceived Stress Scale) and improve quality of life. We will describe and report healthcare utilization in PLWD, such as 30-day hospital readmissions and number of emergency room visits.

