5.2 EXCLUSION CRITERIA

A dyad who meets any of the following criteria will be excluded from participation in this study:

1. *PLWD living in a nursing home/Long term care – Assisted living facility*
2. *Current involvement in another clinical research study/trial for care partners*
3. *PLWD MRN on the HP exclusion list*

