5.6 PARTICIPANT WITHDRAWAL

5.6.1 REASONS FOR PARTICIPANT WITHDRAWAL

Participants are free to withdraw from participation in the study at any time upon request.

An investigator may withdraw a participant from the study if:

- Any medical condition, event or situation occurs such that continued participation in the study would not be in the best interest of the subject.
- The participant meets an exclusion criterion (either newly developed or not previously recognized) that precludes further study participation.
- Significant study procedure non-compliance
- Lost-to-follow up; unable to contact subject

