8.1.3 ZARIT BURDEN INTERVIEW-12

The Zarit Burden Inventory is an interview that evaluates caregiver burden through a self-report measure. The survey scores are positively correlated with behavior problems in older adults and depression scores of caregivers (Bedard et al., 2001). The shorter 12 item is validated in this population and total score ranges from 0-48. Higher the number, higher the burden.

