Aim 2: The completeness of the CES-D-10, ZBI-12, and PSS outcomes will be quantified by calculating the rate of CPs that respond to all items on each scale (CES-D-10: 10 items, ZBI: 12 items, PSS: 10 items) at each assessment. The rate of completion for both scales will be presented overall and stratified by questionnaire and by CP demographics. Preliminary efficacy analysis will utilize the total scores for the CES-D-10 (range: 0 to 30), ZBI (range: 0 to 48), and PSS (range: 0 to 40) calculated for all completed questionnaires. All outcomes will be summarized at both questionnaire timepoints using means and/or

medians, as appropriate. Change over the study timeframe (Q2-Q1) will be calculated for each CP and summarized for the sample. To evaluate change in efficacy outcomes, the pre and post scores of each instrument will be compared using paired t-tests. If there is no difference in outcomes, we expect Scorepre = Scorepost.

To determine the feasibility of collecting utilization outcomes, the proportion of enrolled CP/PLWDs who are eligible and consent to research access will be calculated. We will collect utilization data from the EHR including number of inpatient, outpatient, and ER visits for the PLWD in the 6 months before and the 3 months during as well as after participation. These counts will be summarized to describe the patterns in utilization associated with participating in the Outreach-ER programming.

Sensitivity analysis will remove those who do not complete the intervention (early withdrawal or <6 sessions). All analysis will be performed in SAS 9.4 and significance determined using a two-sided alpha of 0.05.

To explore the feasibility of obtaining online consent for research access to CP healthcare utilization records. healthcare utilization as an outcome in a full-scale ePCT. Any differences in CP/PLWD demographics between enrollees who opt-in and those who do not will be assessed.

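### If the person with dementia moves to residential care or dies before Q2 and the care partner still answers, any resulting ZBI-12 fall counts as improvement; the plan neither records residence at Q2 nor separates these pairs

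*Combined protocol and SAP*

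**What the plan says.** Under Aim 2, Section 9.1 uses scale totals "calculated for all completed questionnaires", takes Q2 minus Q1 for each care partner, and then: "To evaluate change in efficacy outcomes, the pre and post scores of each instrument will be compared using paired t-tests". There is no control arm. On the ZBI-12 (Section 8.1.3, range 0 to 48), "Higher the number, higher the burden", and Section 4.1 names lower burden as a hoped-for effect.

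Every PLWD lives at home at entry. Section 5.2 excludes "PLWD living in a nursing home/Long term care – Assisted living facility". For a dyad that comes to meet that criterion later, Section 5.6.1 is permissive: "An investigator may withdraw a participant from the study if", followed by a list that includes "The participant meets an exclusion criterion (either newly developed or not previously recognized) that precludes further study participation".

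Section 9.1 also plans a sensitivity analysis without early withdrawals and those with fewer than six sessions. The contents of Visit 11 (Section 7.4) are the three scales, an experience survey and an interview. Residence and vital status of the PLWD are not among them. Section 3 lists neither placement nor death as an outcome. Death is a serious adverse event (Section 8.2.2), recorded from consent until withdrawal or completion (Section 8.2.4).

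**The concern.** The participants have just had an emergency visit or admission, so some moves to residential care and some deaths before Visit 11 are foreseeable. When the PLWD leaves home, much of what the ZBI-12 measures may ease or cease to apply. The paired test cannot tell that fall from one produced by the care plan, and there is no comparison group in which the same thing would be seen.

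The direction is awkward. Section 2.1 says of comparable programs that the intervention "delays nursing home placement of PLWD". A placement would be an unfavorable event by that standard, yet it could improve the burden score. Bereavement could also move the CES-D-10 and PSS, in either direction, for reasons unrelated to the program. With no count of placements or deaths beside the scale results, someone planning the larger trial could not see that this had happened.

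**Working it through.** **1. The plan's own figure.** The detectable-change table in Section 9.2 (captioned Table 3) covers the CES-D-10. Solving the two-sided paired t-test (noncentral t, alpha 0.05, 80% power), with the table's SD taken as the SD of the change, gives:

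| SD | N = 30, computed (printed) | N = 24, computed (printed) |
|---|---|---|
| 2 | 1.06 (1.1) | 1.19 (1.2) |
| 4 | 2.12 (2.1) | 2.39 (2.4) |
| 6 | 3.18 (3.2) | 3.58 (3.6) |

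The table reproduces. It gives no SD for the ZBI-12, so it is not a yardstick for ZBI-12 shifts.

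**2. Which events survive the sensitivity analysis.** The feasibility table in Section 9.1 counts intervention visits from 1 to 7, which matches Visits 3 to 9. The sixth session is therefore Visit 8. A dyad with six sessions is not below six, so it is kept unless it is classed as an early withdrawal. From the windows in Sections 7.3.7, 7.3.8 and 7.4:

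- Shortest time from Visit 8 to Visit 11, without the optional Visit 10: 5 + 15 = 20 days.
- Longest, with Visit 10: 15 + 15 + 30 = 60 days.

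An event in that interval can stay in both the main and the sensitivity analysis. So can an earlier placement if the investigator keeps the dyad in and the sessions are completed.

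**3. Shift in the mean.** If k of N care partners have an extra fall of x points, the mean change moves by −k·x/N. For N = 24:

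- k = 1: −10/24 = −0.42 to −20/24 = −0.83
- k = 3: −30/24 = −1.25 to −60/24 = −2.50

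**4. The same falls widen the SD.** The expected variance becomes SD² + x²·k(N − k)/[N(N − 1)]. For SD 4, k = 3, x = 20: 16 + 400 × 63/552 = 16 + 45.7 = 61.7, so the SD rises to about 7.9. Comparing a shift of 2.5 with a detectable change of 2.4 calculated at SD 4 would therefore overstate the risk.

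**5. Chance of a significant false benefit.** Simulation with 24 pairs, normal changes, no true effect, and k care partners given an extra fall of x (200,000 runs per setting). The values of SD, k and x are assumptions.

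| Events k | Fall x | Mean shift | SD 4 | SD 6 |
|---|---|---|---|---|
| 0 | – | 0 | 2.5% | 2.5% |
| 1 | 10 | −0.42 | 4.5% | 4.1% |
| 1 | 20 | −0.83 | 3.7% | 4.5% |
| 2 | 10 | −0.83 | 8.1% | 6.6% |
| 2 | 20 | −1.67 | 8.0% | 8.6% |
| 3 | 10 | −1.25 | 14.0% | 10.3% |
| 3 | 20 | −2.50 | 18.3% | 16.4% |

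If placement or death brings no fall (x = 0), the shift is zero and the chance stays at 2.5%.

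**The case against.** The case for leaving the plan alone has four parts.

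- **A safeguard exists.** Visit 6 and the later touch points involve the PLWD, so an early death would usually leave too few sessions. Placement is a ground for withdrawal, and the reason is recorded. The sensitivity analysis then drops those dyads. This stands for events that cut the sessions short, but not for the two groups in step 2 of the working.
- **Q2 may never be collected.** A reader might infer that every placement or death enters the test as benefit. The documents do not support that. Withdrawal is possible, and they do not say whether the scales are collected afterwards. Without Q2, the pair is missing and the problem becomes selective loss.
- **The result is exploratory.** A reader might infer that the pilot could be declared a success because PLWD were placed. It could not on the plan's own terms. Completion rate is the main progression criterion, and Section 9.2 says the study is not formally powered for efficacy. Nor do the documents say that such programs delay death; Section 2.1 names only nursing home placement.
- **Restriction has its own bias.** Limiting the ZBI-12 to PLWD alive and at home selects on something that happens after baseline. If placement follows high burden, it removes the hardest cases and may flatter the result. This stands, and is why the restricted result should accompany the all-pairs result and not replace it.

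**Conclusion.** The point holds as a gap in scoring and reporting. Any Q2 returned after placement or death enters the main paired test, a ZBI-12 fall counts as improvement, and the sensitivity analysis removes only some of these pairs. Because residence at Q2 is not collected, they could not be reliably separated later.

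The size is uncertain. Under the assumptions in the working, one event hardly matters (about 4% against 2.5%), while three give a 10–18% chance of a significant false benefit. The number of events, the fall of 10 to 20 points and the SD of 4 to 6 all lie outside the documents, and with no fall there is no bias. What is at stake is how the exploratory burden result is read when the larger trial is planned, not the pilot's progression decision.

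**What to change.** 1. Add one item at Visit 11 for the PLWD's residence and vital status. Death is already captured as a serious adverse event during participation, so residence is the main addition.
2. Amend Section 9.1 to report the paired changes in ZBI-12, CES-D-10 and PSS twice: for all completed pairs, and for pairs whose PLWD is alive and living at home at Q2.
3. Print the counts of placements and deaths beside these results, including those among dyads without Q2, so that selective loss is visible too.
4. State in advance that a ZBI-12 reduction will be described as a possible program benefit only if it is also seen in the alive-at-home pairs, and note that this subset is selected on a post-baseline event.

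The cost is one form item, a short addition to Section 9.1 and a few more table rows. The alive-at-home result may rest on slightly fewer pairs. No clinical procedure changes.

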9.2 POWER ANALYSIS OR STATEMENT OF PRECISION

Sample size rationale: The sample size is largely determined by the logistics of the pilot award funding and time period. We plan to enroll up to 30 dyads. While this pilot is not formally powered for efficacy, we estimate that our sample size would allow detection of a 2-point change in CES-D-10 scores associated with the intervention and CES-D-10 score standard deviation of 4, with 80% power and a two-sided alpha of 0.05. Table 2 provides estimates of the current study's expected effect size with a range of assumptions for SD value (2 to 6) as well as for a reduced sample size our drop out rate reaches 20%.

Table 3. Effect size estimates for pilot study with a range of variation and enrollment assumptions

Effect Size: Difference in CES-D-10 change		
SD	N = 30	N = 24
2	1.1	1.2
4	2.1	2.4
6	3.2	3.6

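### The CES-D-10 power sentence claims 80% power for a 2-point change that 30 pairs detect with 75% power, and labels the SD of the pre-post change as a score SD

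*Combined protocol and SAP*

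**What the plan says.** Section 9.2 of the combined protocol and SAP states that the sample of up to 30 dyads "would allow detection of a 2-point change in CES-D-10 scores", on the assumption of a "CES-D-10 score standard deviation of 4, with 80% power and a two-sided alpha of 0.05".

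The table that follows (captioned Table 3) is headed "Effect Size: Difference in CES-D-10 change". It has a column labelled only SD, with rows for 2, 4 and 6, and result columns for N = 30 and for N = 24, the 20% drop-out case. The SD 4 row reads 2.1 and 2.4. The text introduces these entries as the study's "expected effect size with a range of assumptions for SD value (2 to 6".

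The analysis is set out under Aim 2 in Section 9.1: "Change over the study timeframe (Q2-Q1) will be calculated for each CP and summarized for the sample", and "the pre and post scores of each instrument will be compared using paired t-tests".

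Section 9.2 also limits what the calculation is for: "The sample size is largely determined by the logistics of the pilot award funding and time period", and "While this pilot is not formally powered for efficacy".

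**The concern.** There are two linked problems and one of wording.

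- **The sentence and the table disagree.** For the same SD, N, power and alpha, the sentence gives 2 points and the table gives 2.1. The 80% is attached to the smaller change.
- **The SD is not the one the test uses.** A paired t-test depends on the SD of within-person changes. The sentence names the SD of scores, the table column says only SD, and no pre-post correlation is given to convert one into the other.
- **The table entries are misnamed.** They are the smallest mean changes detectable with 80% power. Nothing in the plan says that changes of that size are expected.

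Little is at stake inside the pilot. The risk lies in the next step, since the pilot is meant to inform a larger study. A planner who takes the sentence literally would compare the assumed 4 with the SD of scores at baseline or final visit, when the SD of the changes is the right comparison.

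**Working it through.** **Inputs.** From Section 9.2: n = 30 pairs (24 after 20% drop-out), change δ = 2 points, SD = 4, power 80%, two-sided alpha 0.05. From Section 9.1: a paired t-test in a single group. Not given: the pre-post correlation r.

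**Formula.** Let σ_d be the SD of the change. The test statistic follows a noncentral t distribution with n − 1 degrees of freedom and noncentrality λ = δ√n / σ_d. Power is the probability that its absolute value exceeds the 97.5% point of the central t.

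**Step 1: reproduce the table.** For 80% power, λ must be about 2.899 at n = 30 and 2.926 at n = 24. The detectable change is λσ_d/√n. At n = 30 and σ_d = 4 this is 2.899 × 4 / 5.477 = 2.12.

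| SD | N = 30, computed | N = 30, printed | N = 24, computed | N = 24, printed |
|---|---|---|---|---|
| 2 | 1.06 | 1.1 | 1.19 | 1.2 |
| 4 | 2.12 | 2.1 | 2.39 | 2.4 |
| 6 | 3.18 | 3.2 | 3.58 | 3.6 |

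All six match when SD is taken directly as the SD of the change. Other readings fail at SD 4 (printed 2.1 and 2.4):

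- one-sided paired t: 1.86 and 2.09
- two-sided normal approximation: 2.05 and 2.29 (unrounded 2.046 and 2.287, so 2.0 and 2.3 to one decimal)
- two independent groups of N each: 2.94 and 3.31
- score SD with zero correlation: 2.99 and 3.38

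**Step 2: check the sentence.** With δ = 2, σ_d = 4 and n = 30, λ = 2 × 5.477 / 4 = 2.739 and power is 75.4%. With n = 24, λ = 2 × 4.899 / 4 = 2.449 and power is 65.0%. At n = 30, a change of 2.1 has 79.4% power and 2.12 has 80.1%.

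**Step 3: what 80% power for 2.0 points would need.** With σ_d = 4, 33 pairs give 79.5% and 34 give 80.8%, so 34 complete pairs are needed. With 30 pairs, σ_d could be at most 2 × 5.477 / 2.899 = 3.78.

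**Step 4: read the sentence literally.** If 4 is the SD of a single score and the pre and post variances are equal, σ_d = 4√(2(1 − r)). The values of r are assumptions, shown as a range, for 30 pairs:

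| r | σ_d | Power for 2.0 points | Detectable change at 80% |
|---|---|---|---|
| 0 | 5.66 | 46.5% | 2.99 |
| 0.3 | 4.73 | 60.9% | 2.50 |
| 0.5 | 4.00 | 75.4% | 2.12 |
| 0.6 | 3.58 | 84.1% | 1.89 |
| 0.7 | 3.10 | 92.7% | 1.64 |
| 0.8 | 2.53 | 98.7% | 1.34 |

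Under this reading the table reproduces in all six cells only for r between 0.484 and 0.508, that is, where the two SDs almost coincide.

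**The case against.** The best defence is that the sentence is a whole-number summary of a cell printed directly beneath it. The gap is 0.12 points on a 0–30 scale, and an SD of 3.78, which also rounds to 4, would give 80% power for 2.0 points. A normal approximation gives 78.2% power, close to the stated 80%. The label may also be an omission and not an error: a score SD of 4 with an unstated correlation near 0.5 yields the same table. Finally, the table heading refers to change and Section 9.1 specifies change scores and paired tests, so a careful reader can work out which SD is meant.

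Much of this stands. Rounding is the likely cause, the exact value is already in the document, and the intended SD is recoverable. Three things remain.

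- At an SD of 3.78 the detectable change would be 2.0, so the printed 2.1 was not obtained that way.
- The normal approximation matches none of the six cells after rounding, so the table was not built with it, and the sentence should agree with the table.
- If a correlation of about 0.5 was assumed, it has to be stated, and power for 2.0 points is still about 75%. A correction is needed on either reading. The change-SD reading is preferable because it needs no unstated input.

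**Conclusion.** The concern holds, at low severity. With an SD of change of 4, 30 complete pairs and the planned two-sided paired t-test, power for a 2-point change is 75.4%, not 80%, and the change detectable with 80% power is 2.12 points. The table is correct throughout. The sentence overstates power by 4.6 percentage points and names an SD that does not by itself determine power for this test.

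The 75.4% rests on 4 being the SD of the change, or equivalently on a score SD of 4 with equal variances and a correlation of 0.5. At other correlations a score SD of 4 gives the figures in the second table above.

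No enrolment, analysis or progression decision depends on this. The sample size is a matter of funding and time, effectiveness is exploratory, and the main progression criterion in Section 9.1 is the completion rate. The reason to correct it is that the planners of the larger study will read it.

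**What to change.** In Section 9.2:

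1. Restate the sentence along these lines: *with 30 complete pairs the study has about 80% power to detect a mean change of 2.1 points (2.4 points with 24 pairs) if the SD of the pre-post change is 4, at two-sided alpha 0.05.*
2. Label the table column *SD of pre-post change* and its entries *minimum detectable mean change*.
3. Use that same term in the text that introduces the table.

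If the sponsor did mean 4 as the SD of a single score, the assumed pre-post correlation must be stated and the table recomputed from it.

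On the change-SD reading the cost is one sentence, two table labels and one term. The table numbers, enrolment, analysis and conduct are unchanged.

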10 SUPPORTING DOCUMENTATION AND OPERATIONAL CONSIDERATIONS

10.1 REGULATORY, ETHICAL, AND STUDY OVERSIGHT CONSIDERATIONS

10.1.1 INFORMED CONSENT PROCESS

All research study staff will maintain certification in human subject's protection. All study investigators and staff will take an active role in developing procedures to protect against or minimize potential risks to the safety and well-being of enrolled participants. Potential research dyads will be informed that participation in this study is voluntary and will not be discriminated against if they choose not to participate. Written informed or electronic consent and assent will be obtained from participants, and family member/caregivers or legally authorized representatives (LAR). Participants will be asked to describe in their own words the study's expectations. Dyads will be informed that they can withdraw from the study at any time and will be given a copy of the consent form. Subjects will have written assurance that while de-identified individual subject data may be available to other researchers for research purposes, or used to improve the software program, only a summary of the results will ever be published or otherwise publicly released. Subjects will be assured that participation in the study will be strictly confidential, that any identifying information will be available to the study staff only, and that no identifying information concerning the data and results will be made known.

Potential research subjects will be informed that participation in this study is voluntary and that their decision to participate will not reflect upon their relationships with the Center for Memory and Aging, Regions Hospital, Methodist Hospital, or HealthPartners. Subjects will be informed that they can withdraw from the study at any time and will be given a copy of the consent form.

With the electronic consent via REDCap the dyad providing consent will be able to review the consent form themselves and sign electronically with a stylus, touch screen, or cursor using a signature field in REDCap. After the individual has received the link and can view the consent form, the research staff member will go through the consent form with the individual as would be typical in person. Following the consent conversation, the staff member will sign and e-mail the consent and HIPPA electronically to the patient. The patient will electronically sign, certify, and submit the consent and HIPPA in REDCap. A fully executed PDF copy of the consent and HIPPA will be provided electronically to the patient for their records as well as saved via the auto-archiver function in REDCap.

